**1. SUMMARY OF THE STUDY**

Within the scope of the research, an experimental group of 14 people and a control group of 20 people will be determined. The "Chrisofix External Fixator" fixation orthosis will be applied externally to the rib rib-fracture area along with standard medical treatment to the experimental group, and standard treatment-medical treatment will be applied to the control group. Within the scope of the research, treatment times, difference between initial pain levels and discharge pain levels, and return to work times between these groups will be compared. It is expected that the Chrisofix External Fixator applied as a result of the project will shorten the treatment time, reduce pain and accelerate the return to work process.

**2. JUSTIFICATION AND OBJECTIVES OF THE STUDY**

**Introduction and Rationale of the Study:**

The aim of the study is to shorten the recovery time in rib fracture cases with external fixation treatment, increase comfort, reduce pain level, provide a significant decrease in the time it takes for patients to return to daily life, and reduce rib fracture-related complications in patients.

**Main Purpose of the Study**

The aim of the study is to shorten the recovery time in rib fracture cases with external fixation treatment, increase comfort, reduce pain level, provide a significant decrease in the time it takes for patients to return to daily life, and reduce rib fracture-related complications in patients.

**Secondary Purpose of the Study**

**3. HYPOTHESIS OF THE STUDY**

- 1) External fixation reduces the pain level in cases with rib fractures
- 2) External fixation shortens the hospital stay in cases with rib fractures
- 2) External fixation reduces the development of complications in cases with rib fractures

**4. POPULATION TO BE RESEARCHED & SELECTION OF VOLUNTEERS**

Date/ Version: 11.06.2020

Protocol Information Form for Non-Pharmaceutical Studies	Document Code	Rev. Date / Number:	Page
	Form 16	03.11.2010/EÜTF00	2/6

**Protocol Name/Code:** Comparative Evaluation of External Chest Wall Fixator Treatment Effectiveness in Patients With Rib Fractures

Disease Name	Rib fracture		
Number of Volunteers and Characteristics	Sağlıklı : Hasta (Hastalığın adı) : Toplam sayı :	Kadın : 0 Erkek : 15 15	Yaş aralığı : - 20-50 20-50
Regulations Regarding the Participation of Volunteers in the Study			
Volunteers will consist of patients who applied to Ege University Faculty of Medicine Hospital after trauma and were admitted to the Thoracic Surgery service and who agreed to participate in the study.			
Criteria for Inclusion in the Study			

 
Patients with serial rib fractures after trauma
 
Patients without extrathoracic pathology
 
			
Criteria for Exclusion from the Study			

 
Patients with less than 3 rib fractures
 
Patients with extrathoracic injuries
 
Patients with bilateral rib fractures
 
Patients with flail chest
 
Patients with hemothorax or pneumothorax requiring drainage with tube thoracostomy at first admission
 
			
Criteria for Exclusion from the Study and Procedures to be Followed in This Case			
Volunteers can leave the study at any stage of the study. Volunteers who have problems completing any of the study steps may be excluded from the study. Follow-up of individuals who withdraw or are excluded from the study will continue as should be in routine practice.			

5. STUDY DESIGN & METHOD
Study Design
Patients who were admitted due to trauma and had serial rib fractures were evaluated. There were 14 patients in case group and 20 in control group.
Details of Working Method
Standard treatment was applied to the control group. External chest wall fixator was applied to the case group in addition to standard treatment. Pain levels of the patients, development of complications and duration of hospitalization were recorded. Pain levels of the patients were evaluated using the Visual Analogue Scale and the pain level was scored between 0 and 10.
Defining Transactions During Working Days & Visits
The patient's pain level will be recorded using the Visual Analogue Pain Scale during visits on the day of admission and the day of discharge.
Randomization Method and Its Importance (if any)
None
Blindness Method & Importance (if any)

Date/ Version: 11.06.2020

Protocol Information Form for Non-Pharmaceutical Studies	Document Code	Rev. Date / Number:	Page
	Form 16	03.11.2010/EÜTF00	3/6

**Protocol Name/Code:** Comparative Evaluation of External Chest Wall Fixator Treatment Effectiveness in Patients With Rib Fractures

None

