**Materials to be Used & Storage Conditions & Responsibilities**

**6. COLLECTION OF STUDY DATA**

**Recording Data/Case Report Forms**

The data of the patients will be recorded with case report forms during the days they stay in the thoracic surgery service.

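### The pain sections conflict on when VAS is measured, and the only scheduled follow-up value falls on the discharge day, which the fixator is expected to move

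*Combined protocol and SAP*

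**What the plan says.** Section 1 (Summary) says the groups will be compared on the "difference between initial pain levels and discharge pain levels", alongside treatment time and return to work. It expects that the fixator "will shorten the treatment time, reduce pain and accelerate the return to work process".

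Section 3 lists pain reduction as the first hypothesis, with no time point. A further hypothesis reads "External fixation shortens the hospital stay in cases with rib fractures".

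Section 5, under the heading on visits, schedules the "Visual Analogue Pain Scale during visits on the day of admission and the day of discharge" and no other pain assessment. Its working-method paragraph says "Pain levels of the patients, development of complications and duration of hospitalization were recorded", without times. It also states that there is neither randomisation nor blinding, and gives the group sizes: "There were 14 patients in case group and 20 in control group".

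Section 6 has data "recorded with case report forms during the days they stay in the thoracic surgery service". Its Evaluation Criteria then list pain on the 10th day, at the 1st month and at the 3rd month, together with complications and length of stay. Discharge pain is not in that list, and the day from which the 10th day is counted is not given.

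Section 10 names chi-square, Mann-Whitney and Spearman methods at the 0.05 level. None of them accounts for when a pain score was taken.

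**The concern.** The pain change described in the summary is not an evaluation criterion, and the pain values that are evaluation criteria are not scheduled. A reader cannot tell which comparison answers the pain hypothesis, or whether the data for it will exist.

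The timing matters because pain after a rib fracture would normally be expected to fall with time, while the stay hypothesis says the fixator brings discharge forward. If it does, the second VAS is taken sooner after admission in the fixator group. The direction of the error then depends on why patients leave, and the documents give no discharge rule:

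- If patients leave once pain is tolerable, discharge scores are pulled together in both groups and a pain benefit is hidden.
- If patients leave sooner for other reasons, the fixator group is read higher on its recovery curve and the device looks worse.

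What is at stake is the answer to the pain hypothesis. In the first case the planned length-of-stay comparison would still show that the device helped.

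**Working it through.** **Step 1: the sections side by side.**

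| Pain value | Compared (Section 1) | Scheduled (Section 5) | Listed criterion (Section 6) | Route after discharge |
|---|---|---|---|---|
| Admission | yes | yes | no | not needed |
| Discharge | yes | yes | no | not needed |
| 10th day | no | no | yes | none stated |
| 1st month | no | no | yes | none stated |
| 3rd month | no | no | yes | none stated |

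Later collection is not forbidden, but no visit, call or form provides for it. If day-10 values are taken only on the ward, they exist only for patients still there.

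**Step 2: what can be reproduced.** The stated sample size is 34 = 14 + 20. No SD, effect size, pain curve or discharge rule is given, so the size of any timing bias cannot be derived. What follows is illustration.

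**Step 3: assumed inputs (none from the documents except 14 vs 20 patients, Mann-Whitney and the 0.05 level, taken as two-sided).** True VAS at day t is a·exp(−k·t), with a normal (mean 8, SD 1, kept within 0-10). The rate k is a median rate with log-normal variation 0.35. Measurement SD is 0.7. There were 4,000 simulated trials per scenario (Monte Carlo error at most 0.8 percentage points).

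**Step 4: discharge follows pain** (first whole day with true VAS 3 or less), control rate 0.11/day. Hand check of median stay: ln(8/3)/0.11 = 8.9 days, and ln(8/3)/0.18 = 5.4 days for the fastest fixator rate. Simulated mean stays were 9.9 and 6.2 days.

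| Fixator rate per day | Change to discharge | Day-10 VAS, all patients | Length of stay |
|---|---|---|---|
| 0.18 | 6% | 83% | 94% |
| 0.15 | 5% | 44% | 59% |
| 0.13 | 5% | 18% | 22% |

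Entries are power. At 0.18/day with measurement SD 1.5, the three figures become 5%, 47% and 93%.

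If day-10 VAS is taken only on the ward (0.18/day), 8% of fixator and 47% of control patients have a value. That is 0.082 × 14 = 1.1 and 0.474 × 20 = 9.5 patients. About 30% of trials have no fixator value at all (check: 0.918^14 = 0.30). The group gap shrinks from 2.68 − 1.43 = 1.25 points to 3.55 − 3.20 = 0.35.

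**Step 5: discharge not driven by pain, no true pain effect**, rate 0.11/day in both groups, control mean discharge day 8. Hand check for day 5, without rate variation: 8·exp(−0.55) − 8·exp(−0.88) = 4.62 − 3.32 = 1.30 points of apparent harm.

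| Fixator mean discharge day | Apparent harm (points) | Significant false harm, discharge-day SD 0 / 2 / 3 |
|---|---|---|
| 8 | 0 | about 2% throughout |
| 7 | 0.4 | 9% / 8% / 7% |
| 6 | 0.8 | 30% / 25% / 20% |
| 5 | 1.2-1.3 | 64% / 53% / 42% |

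Day-10 VAS in all patients gives about 2% false harm throughout.

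**Step 6: true benefit (0.15 vs 0.11/day), discharge not driven by pain, discharge-day SD 2.** Change to discharge shows a significant benefit in 27%, 10%, 2% and 0.3% of trials when the fixator mean day is 8, 7, 6 and 5. Day-10 VAS shows it in about 45%.

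**The case against.** The strongest reply is that the Evaluation Criteria are the plan's own list of what is evaluated. They already name three fixed times, and Section 10 does not restrict its tests to the contrast in the summary. On that reading, fixed-day pain is intended and Sections 1 and 5 are merely incomplete. This stands as a fair reading. A reader might infer that the plan has settled on a discharge-based endpoint, or that change to discharge is its only pain comparison; the documents support neither. But intention does not collect data. As scheduled, the fixed-day values would be missing, or would exist only for longer stays.

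The illustration can also be challenged, with some force. The rule in Step 4 makes discharge scores similar almost by construction, and length of stay there detects the benefit better than day-10 VAS does. The large false-harm figures need discharge three days earlier for reasons unrelated to pain; one day gives only 7-9%. With measurement SD 1.5 the power of day-10 VAS falls to 47%. The figures therefore show mechanism and direction, not the trial's bias.

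Finally, a fixed day does not make the comparison sound. Allocation is not randomised and nobody is blinded. In a check with no device effect, a fixator group recovering faster through selection alone (0.13 vs 0.11/day) gave 16% false positives on raw day-10 VAS and 18% after adjustment for admission VAS. Measuring some patients at home and others on the ward could add a difference in mode between groups. These limits are real, but they do not justify leaving the timing unresolved.

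**Conclusion.** The concern holds in two parts of different strength.

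**Certain from the text:** Sections 1, 5 and 6 disagree on which pain values are compared, scheduled and evaluated. The 10th day has no stated origin, and there is no stated route for collecting pain after the ward stay.

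**Conditional:** if the stay hypothesis is true, change to discharge alone can give a misleading answer on pain, by masking a benefit or by suggesting harm. If stays are equal, this bias is absent. A reader might conclude that the trial's pain result will be biased by a known amount or in a known direction. The documents do not support that, because they give no discharge rule, pain curve or SD. The ranges in the working rest wholly on the assumed curve, variation and discharge gaps.

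This should be fixed. The certain part is enough to require reconciliation, and the conditional part is a reason to reconcile towards a fixed time.

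**What to change.** Reconcile Sections 1, 5 and 6 so that the pain hypothesis is compared at one fixed time already in the Evaluation Criteria, counted from admission and named before analysis. Which listed time to use is the investigator's choice. Record it in every patient, discharged or not, by the same mode in both groups as far as possible, and provide a form for it. The Mann-Whitney test already planned is sufficient. Adjustment for admission VAS is optional and does not cure selection. Report discharge VAS descriptively beside length of stay.

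Sections 5 and 11 are partly in the past tense, so collection may be finished. In that case, analyse fixed-day VAS where it exists, report missing values by group, and do not interpret change to discharge alone as a test of the pain hypothesis.

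The cost is wording, one short contact for patients already home, and possibly ethics committee approval under the protocol-changes paragraph of Section 11. If day 10 were chosen, the Step 4 illustration (0.18/day) puts about 0.918 × 14 + 0.526 × 20 = 23 of 34 patients at home by then, with a range of about 20 to 31 under other assumed inputs.

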**Ensuring Patient Compliance**

Patients will be informed by us when they are admitted to the Thoracic Surgery service, they will be asked if they want to participate in the study, and if they want to participate, they will have to sign an informed consent form. If the patient does not want to participate in the study, he will be hospitalized again and standard medical treatment for rib fracture will be applied.

**Materials to be Used & Storage Conditions & Responsibilities**

**6. COLLECTION OF STUDY DATA**

**Recording Data/Case Report Forms**

The data of the patients will be recorded with case report forms during the days they stay in the thoracic surgery service.

**Interpretation and Reporting Methods**

Visual Analog Scale (VAS) will be used to determine the pain level of the patients.

**Evaluation Criteria**

Number/location of rib fractures

unclassified incident

Accident Type

Pathology accompanying rib fracture

Pain level on the 10th day

1st month pain level

3rd month pain level

development of complications

Length of hospital stay

**7. SURGICAL PROCEDURES (if applicable)**

None

**8. PRECAUTIONS & WARNINGS TO ENSURE VOLUNTEER SAFETY**

**9. CONDITIONS WHICH MAY REQUIRE SUSPENSION OF OPERATION**

**10. STATISTICAL PROCEDURES**

**Sample Size**

34

**Statistical and Analytical Methods**

Date/ Version: 11.06.2020

Protocol Information Form for Non-Pharmaceutical Studies	Document Code	Rev. Date / Number:	Page
	Form 16	03.11.2010/EÜTF00	4/6

**Protocol Name/Code:** Comparative Evaluation of External Chest Wall Fixator Treatment Effectiveness in Patients With Rib Fractures

For categorical variables in descriptive analyses; number and percentage values for continuous variables; Mean, standard deviation, min-max and range values will be presented.

Kolmogorov-Smirnov and Shapiro Wilk tests will be performed to examine compliance with normal distribution. Chi-square, Mann Whitney U test and Spearman rank correlation will be used to examine the statistical relationship between groups.

Statistical significance level will be determined as  $p < 0.05$ .

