**Informing Patients and Informed Volunteer Consent**

Informed consent form was obtained from each patient to be included in the study.

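### Groups are not randomised and no allocation rule is given, yet only unadjusted tests are planned, so a severity imbalance could mimic or mask a fixator effect, most clearly on hospital stay

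*Combined protocol and SAP*

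**What the plan says.** All references are to the combined protocol and SAP.

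- **Allocation.** In Section 5, the field beginning "Randomization Method and Its Importance (if any" is answered None. The group sizes are given without an assignment rule: "There were 14 patients in case group and 20 in control group". Section 1 gives the same sizes, also without a rule.
- **Patients who decline.** Ensuring Patient Compliance says of such a patient that "he will be hospitalized again and standard medical treatment for rib fracture will be applied". It does not say whether these patients are the controls. Section 11 says "Informed consent form was obtained from each patient to be included in the study".
- **Hypotheses.** Section 3 is worded causally, for example "External fixation shortens the hospital stay in cases with rib fractures".
- **Eligibility.** Section 4 excludes "Patients with less than 3 rib fractures", and also bilateral fractures, flail chest, extrathoracic injury, and haemothorax or pneumothorax needing a tube at first admission.
- **Severity data.** Evaluation Criteria in Section 6 lists "Number/location of rib fractures" and accompanying pathology. Section 5 has pain on the VAS recorded on the days of admission and discharge.
- **Analysis.** Section 10 gives descriptive statistics, normality tests, a 0.05 significance level and this: "Chi-square, Mann Whitney U test and Spearman rank correlation will be used to examine the statistical relationship between groups". No regression, stratification, matching or propensity method appears.

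**The concern.** Without randomisation, the two groups may differ in how badly the patients were injured, and a reader cannot judge how likely that is without knowing who decided which patients received the fixator. If the fixator group was less severely injured, it would leave hospital sooner with no device effect. If it was more severely injured, a real effect could be hidden. The planned tests compare the groups as they stand, so a p-value below 0.05 for stay would not separate the device from severity. Spearman correlation could relate rib count to stay, but it does not adjust the group comparison.

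The eligibility rules narrow severity without balancing it. There is a floor of three fractures but no upper limit, and fracture location and accompanying pathology can still differ. The plan records these variables and gives them no role in the comparison.

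Hospital stay is the clearest case because it has no baseline value. Pain has an admission value and Section 1 compares the admission-to-discharge difference, but that removes bias only under an assumption set out below.

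**Working it through.** **The plan's own figure.** The sample size of 34 equals 14 + 20. No effect size, SD or power is stated, so there is no calculation to reproduce.

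**Inputs.** From the documents: 14 and 20 patients, 0.05 level, Mann-Whitney test. Assumed: two-sided testing, severity-stay correlation r = 0.3 to 0.6, severity imbalance d = 0.25 to 0.75 SD. The documents give neither r nor d.

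**Hand check, no true effect.** The apparent group difference in stay, in SD units, is r × d. Its standard error is √(1/14 + 1/20) = 0.348. At r = 0.5 and d = 0.5 the shift is 0.25 SD, and 0.25/0.348 = 0.717. The rejection rate is P(Z > 1.96 − 0.717) + P(Z < −1.96 − 0.717) = 0.107 + 0.004 = 11%. Simulation of the Mann-Whitney test gives 10%; the rank test rejects slightly less often than this normal approximation.

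**In natural units.** If log stay has an SD of 0.5 (assumed), the apparent stay ratio at d = 0.5 is exp(−0.5 × r × 0.5). This is 0.93 at r = 0.3 and 0.86 at r = 0.6, so stay looks 7-14% shorter with no device effect.

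**Hand check, masking.** With a true effect of 0.8 SD and no imbalance, 0.8/0.348 = 2.30, giving 63% power by the normal approximation and about 57% for Mann-Whitney by simulation. If the fixator group is 0.5 SD more severe and r = 0.5, the visible effect is 0.8 − 0.25 = 0.55 SD. Then 0.55/0.348 = 1.58 and power is 35% by the approximation, 31% by simulation.

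**Simulated Mann-Whitney results, r = 0.3 to 0.6:**

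| Imbalance | Rejection, no true effect (fixator group less severe) | Power, true effect 0.8 SD (fixator group more severe) |
|---|---|---|
| None | about 5% | about 57% |
| 0.25 SD | 5-7% | not run |
| 0.5 SD | 7-12% | 26-41% |
| 0.75 SD | 8-22% | 15-34% |

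**What adjustment recovers.** With a well-measured severity covariate the false-positive rate is about 5%. At 0.75 SD it rises to at most about 7% if the covariate has reliability 0.7, and about 10% at reliability 0.5. Across imbalances of 0.5 and 0.75 SD, adjusted power is about 58-75% with a perfect covariate, 50-60% at reliability 0.7 and 40-51% at reliability 0.5. Part of the gain is variance reduction rather than bias removal: without any imbalance, a perfect covariate already raises power from about 57% to 63-77%.

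**Pain, no device effect, admission pain lower by 0.5 SD in the fixator group.** If discharge pain depends only on admission pain, the change score rejects in 9-12% of runs (against the device) and analysis of covariance in about 5%. If the group difference would simply persist, the change score rejects in about 5% and analysis of covariance in 10-16% (in favour of the device). The documents cannot show which assumption holds.

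**The case against.** The strongest reply is that no imbalance is shown, and that every error rate above depends on assumed inputs. That stands. At 0.25 SD the excess is trivial, and eligibility narrows severity by an unknown amount. The volunteer table in Section 4 (men only, age 20-50) may narrow it further, although its total of 15 conflicts with 34. Yet 0.5 SD is not extreme: even pure chance allocation would exceed it in one direction or the other with probability 2 × P(Z > 0.5/0.348) = 15%.

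A second reply is that adjustment is weak at n = 34. This stands in part. Rib count omits location and accompanying pathology, so the imperfect-covariate figures are the fairer guide, and unmeasured selection remains.

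Two stronger readings are tempting. A reader might infer that patients who refused the fixator form the control group. The documents do not say so, and the statement that every included patient consented points the other way. It still leaves open how consenting patients were divided. A reader might also infer that two agreeing pain analyses would make the result robust. They would not. If the groups would have diverged by 0.5 SD without the device, both analyses wrongly favour it together in about 17-31% of runs. Requiring both to be significant also leaves only about 10-51% power at a true 0.8 SD effect when the groups are imbalanced.

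**Conclusion.** The point holds as a gap in the plan, and it should be fixed. Randomisation is absent, no allocation rule is visible, and the only between-group methods are unadjusted, while the hypotheses are causal. Confidence is high in that reading of the text, but not in any single error rate: these are illustrations for 14 versus 20 patients under assumed correlations and imbalances.

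The documents do not support saying that the groups are imbalanced, that the result is biased, or in which direction. Nor do they support a claim of materially inflated type I error for complications; none is made here. Adjustment for rib count would reduce the problem for hospital stay without removing it.

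**What to change.** 1. **Section 5.** State how patients were assigned to each group, and whether those who decline serve as controls.
2. **Section 10, baseline.** Tabulate number and location of rib fractures, accompanying pathology and admission VAS by group. Judge imbalance by the size of the difference, not by a p-value.
3. **Hospital stay.** Make the main comparison a log or ordinal regression on group and number of fractured ribs, with a 95% confidence interval. Add admission VAS only if it is recorded before the fixator is applied; Section 5 fixes only the day. Keep Mann-Whitney as the unadjusted sensitivity analysis.
4. **Pain.** Report both the admission-to-discharge change and discharge VAS adjusted for admission VAS and rib count, each with a 95% confidence interval and its assumption stated. Use no joint-significance or agreement rule.
5. **Conclusions.** Word them as associations. Sections 5 and 11 are partly in the past tense; if outcome data have been seen, label the adjusted analyses as not pre-specified.

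The cost is wording plus modest extra analysis of variables already recorded. The downsides are a modelling assumption, room for only one or two covariates at n = 34, and residual confounding because rib count measures severity imperfectly.

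Return to work and pain at day 10, month 1 and month 3 are outside this point. Sections 5 and 6 describe data collection only during the hospital stay, so Sections 1, 5 and 6 must be reconciled before those outcomes are analysed.

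### No primary outcome or testing order is named for three hypotheses and several pain times, so the single p < 0.05 rule does not hold the study's overall error at 5%

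*Combined protocol and SAP*

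**What the plan says.** Section 3 gives three hypotheses of equal standing: "External fixation reduces the pain level in cases with rib fractures"; "External fixation shortens the hospital stay in cases with rib fractures"; and "External fixation reduces the development of complications in cases with rib fractures". The main purpose in Section 2 joins several aims without ranking them, and the heading for a secondary purpose has no text beneath it.

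The summary in Section 1 says that "treatment times, difference between initial pain levels and discharge pain levels, and return to work times between these groups will be compared". The visit description in Section 5 records VAS pain on the days of admission and discharge. The Evaluation Criteria in Section 6 list other pain times, "Pain level on the 10th day", "1st month pain level" and a third-month reading, together with complications and length of stay.

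On analysis, Section 10 states: "Chi-square, Mann Whitney U test and Spearman rank correlation will be used to examine the statistical relationship between groups". The decision rule is "Statistical significance level will be determined as" p < 0.05. No outcome is called primary in the text available, and there is no hierarchy, multiplicity adjustment or exploratory label. The sample size entry is the number 34 alone, so no power calculation points to a primary outcome either.

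**The concern.** With three hypotheses and one unranked threshold, nothing in the plan says which result decides whether the fixator worked. The 5% level then describes each test, not the study.

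Pain is the most exposed. It is the first hypothesis, yet its time point is not fixed: Sections 1 and 5 point to discharge, while Section 6 lists three other times. After the data are in, the most favourable reading could be put forward as the test of that hypothesis, and no pre-stated rule would show that a choice had been made. With 34 patients and no blinding, the plan has little else to guard against selective emphasis.

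**Working it through.** **Inputs from the documents.** The threshold is 0.05 (Section 10). There are three hypotheses (Section 3). The distinct comparisons that could be tested are:
- pain, four ways: admission-to-discharge change (Sections 1 and 5), day 10, month 1 and month 3 (Section 6);
- hospital stay and complications (Sections 3 and 6);
- return to work (Section 1).

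That makes 4 + 2 + 1 = 7. Adding the three hypotheses to the four pain comparisons and return to work would give 8, but would count pain twice.

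**Assumptions not in the documents.** Tests are two-sided (sidedness is not stated), there is no true effect, and the groups differ only by chance. Correlation between outcomes is not given, so a range is shown. The plan states no overall error rate, so there is no figure of its own to reproduce; 0.05 is an input.

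**Any significant result, either direction.** For k independent tests the chance of at least one is 1 − 0.95^k.
- k = 1: 5.0%.
- k = 3: 1 − 0.95³ = 14.3%.
- k = 7: 1 − 0.95⁷ = 30.2%.

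For equally correlated normal test statistics, by simulation:

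| Correlation | 3 tests | 7 tests |
|---|---|---|
| 0 | 14.3% | 30.2% |
| 0.3 | about 14% | about 27% |
| 0.5 | about 13% | about 23% |
| 0.7 | about 11% | about 18% |

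**Check with the planned tests.** Six Mann-Whitney tests and one chi-square test were simulated at 14 against 20 patients, with an assumed 20% complication rate. At least one significant result occurred in 29.1% of trials with independent outcomes. It occurred in 24.2% with correlations of 0.5 among the pain readings and 0.3 elsewhere, in 21.2% with 0.8 and 0.5, and in 13.0% with 0.95 and 0.9. The normal approximation is therefore adequate here.

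**Results favouring the device only.** The hypotheses are directional, so this is the error that would support a false claim of benefit. Each two-sided test contributes 2.5%.
- k = 1: 2.5%.
- k = 3: 1 − 0.975³ = 7.3% if independent; about 7% to 5.5% at correlations 0.3 to 0.7.
- k = 7: 1 − 0.975⁷ = 16.2% if independent; about 14% to 9% at correlations 0.3 to 0.7.

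**Does naming a primary suffice?** Suppose pain is tested at 0.05, and hospital stay and complications are tested by Holm whatever the primary shows. With no true effects, Holm rejects at least one secondary when the smaller p-value is below 0.025. The error across the three hypotheses is then 1 − 0.95 × 0.975² = 9.7% if independent, and about 9% to 8% at correlations 0.3 to 0.7. If the secondaries are tested only after a significant primary, there are two cases. If the primary null is true, any false rejection requires rejecting it, so the error is at most 5%. If it is false, Holm holds the two secondaries at 5%. The gate is what restores 5%.

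**The case against.** **Not every listed item is a planned test.** The Evaluation Criteria stand under data collection and include descriptive items such as the type of accident and the count and site of fractures. Section 1 commits only to treatment times, the admission-to-discharge pain change and return to work. This stands: tests at day 10, month 1 and month 3 are an inference, so the seven-test figure is an upper case. The three-hypothesis figure depends much less on inference, although testing each hypothesis at 0.05 is itself the natural reading of Section 10 and not an explicit statement.

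**A reader might infer that a false claim for the device is up to six times likelier than 5%.** The documents do not support that. Six times (30.2 / 5) needs seven independent tests, yet four would be pain readings on the same patients. It also counts results favouring control. Device-favouring errors are about half as frequent, and their proper comparator is 2.5%.

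**Non-randomised allocation is the larger threat.** Section 5 reports no randomisation and no blinding, so even one pre-named test has no guaranteed 5% error rate. This is true and separate. Multiplicity control does not remove confounding, and confounding is no reason to leave the choice of outcome open.

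**It may be too late.** Parts of Sections 5 and 11 are in the past tense. That may be a translation artefact, but if outcomes had already been seen, naming a primary would be post hoc. The fix allows for this.

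**Conclusion.** The concern holds in a limited form. The plan has three unranked hypotheses, several pain times and one p < 0.05 rule, with no primary outcome or order of testing. Testing the three hypotheses as written gives about a 14% chance of at least one false significant result in either direction (14% to 11% at correlations 0.3 to 0.7). Testing all seven comparisons gives up to 30% (27% to 18%). False results favouring the device run at about half these rates, against 2.5% for a single test.

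The figures rest on two-sided tests, assumed correlations and comparable groups; the last is not assured without randomisation. The absence of a primary outcome is judged on the text available, from which some pages were removed. This should be corrected before the results are interpreted as confirmatory.

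**What to change.** In Section 10:

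1. Name one primary outcome, the admission-to-discharge change in VAS, compared between groups by the planned Mann-Whitney test at two-sided 0.05. Sections 1 and 5 both support this measure.
2. Test hospital stay and complications only if the primary is significant, using Holm: the smaller p-value against 0.025, then the other against 0.05. Error across the three hypotheses then stays at 5%.
3. Report day-10, month-1 and month-3 pain and return to work as supportive estimates with 95% confidence intervals and no claim of significance.
4. Reconcile the pain times in Section 6 with the visit schedule in Section 5. Section 6 also says case report forms are completed during the ward stay, so later readings may not be captured. A day-10 primary is usable only if that measurement is scheduled for all patients. If it were adjusted for admission VAS, a model would have to be named, because the Mann-Whitney test cannot adjust.
5. Record that the choice was made before outcome data were seen. If that cannot be shown, label all results exploratory.

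**Cost.** Items 1 to 3 are wording. The primary test keeps its full 0.05. The secondaries lose some power: a comparison with 80% power at 0.05 has Φ(2.80 − 2.241) ≈ 71% at 0.025, before allowing for the gate, and neither can be claimed if the primary fails. Discharge is also not a fixed time. If length of stay differs between groups, the pain change is measured over different intervals, and the report should say so.
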